10.2.2. Protocol Deviations Related to Immunogenicity Analysis

Changes to the procedures or events, which may impact the quality of the immunogenicity data, will be considered important PDs and will be described within the Clinical Study Report (CSR). This includes any circumstances that

Document: \quintiles.net\Enterprise\Apps\sasdata\SAS\SAS\GlaxoSmithKline\HPV\213749

(HPV9)\Biostatistics\Documentation\SAP\GSK 213749(HPV9-AS04-

001)_WZA97329_SAP_Final_v3.0_02FEB2024.docx

Author: PPD Version Number: 3.0

Version Date: 02FEB2024

Template No.: CS_TP_BS016 Revision 7 Reference: CS_WI_BS005

Page 32 of 48

could alter the evaluation of the immunogenicity results such as sample processing errors that lead to inaccurate immunogenicity results, and/or inaccurate dosing which could exclude them from the PPS. In addition, participants may also be eliminated from the PPS based on usage of certain concomitant therapies or vaccines as described in Section 5.2.2 of the Protocol.

11. DEMOGRAPHIC AND OTHER BASELINE CHARACTERISTICS

Demographic data and other baseline characteristics will be presented for the ES and each of the PPS. No statistical testing will be carried out for demographic or other baseline characteristics. The following demographic and other baseline characteristics will be reported for this study:

- Age (years) calculated relative to date of first vaccination
- Age category -<18 and >=18
- Race (as per Clinical Data Interchange Standards Consortium [CDISC] categories)
- Ethnicity

12. GENERAL MEDICAL HISTORY AND EXAMINATIONS

Medical/Vaccination History information will be presented for the ENR.

- Medical History will be coded using Medical Dictionary for Regulatory Activities (MedDRA) central coding dictionary, Version 26.0 or higher.
- Data captured on the "Medical History" page of the eCRF will be presented by System Organ Class (SOC) and Preferred Term (PT). Medical occurrences that begin before the start of study intervention but after obtaining informed consent will be recorded on the Medical History section of the eCRF, not the AE section.

Data will be presented in table summaries for general medical/vaccination history for the ENR and in listings.

13. PRIOR AND CONCOMITANT VACCINATIONS

Prior and concomitant and co-administered vaccination will be coded with the current version of the WHO drug dictionary.

• Prior vaccinations are vaccinations per protocol given to participants prior to the dosing of study intervention and are recorded on the eCRF.

Document: \\quintiles.net\Enterprise\Apps\sasdata\SAS\\SAS\GlaxoSmithKline\HPV\213749

(HPV9)\Biostatistics\Documentation\SAP\GSK_213749(HPV9-AS04-

001)_WZA97329_SAP_Final_v3.0_02FEB2024.docx

Author: PPD Version Number: 3.0

Version Date: 02FEB2024

Template No.: CS_TP_BS016 Revision 7 Reference: CS_WI_BS005

Page 33 of 48

• Concomitant vaccinations are defined as any vaccine that the participant is receiving as of the time of enrolment or receives during the study (other than study interventions) as recorded on the "Concomitant Medications/Vaccination" page of the eCRF, under the "Concomitant Vaccination" category.

Data will be presented in table summaries for concomitant vaccinations for the ES and in listings.

14. MEDICATIONS

The percentage of participants who started medications after study vaccination will be presented by intervention group for the ES.

See APPENDIX 2 for handling of partial dates for medications, in the case where it is not possible to define a medication as prior or concomitant, the medication will be classified by the worst case; i.e., concomitant.

- 'Prior' medications are medications which started prior to the dose of study vaccination.
- 'Concomitant' medications are medications which started on or after the day of the administration of study vaccination

Further details are in Section 6.8 of the Protocol. Concomitant medications during the study will be presented in table summaries (Any, any antipyretic, any prophylactic antipyretic, any antibiotic) and in listings for all medications.

15. STUDY VACCINATION EXPOSURE

Exposure to study vaccine will be presented for the ES. Summaries will include the number of participants with exactly 1 dose, exactly 2 doses, exactly 3 doses, at least 1 dose and at least 2 doses. The date and time of study vaccine administration will be taken from the eCRF "Exposure" form. For dosing instructions and route, refer to Table 6 of the Protocol.

Data will also be presented in listings.

Document: \quintiles.net\Enterprise\Apps\sasdata\SAS\SAS\GlaxoSmithKline\HPV\213749

(HPV9)\Biostatistics\Documentation\SAP\GSK_213749(HPV9-AS04-

001)_WZA97329_SAP_Final_v3.0_02FEB2024.docx

Author: PPD Version Number: 3.0

Version Date: 02FEB2024

Template No.: CS_TP_BS016 Revision 7 Reference: CS_WI_BS005

Page 34 of 48

16. IMMUNOGENICITY OUTCOMES

16.1. Primary Immunogenicity

16.1.1. Primary Immunogenicity Variables & Derivations

The primary immunogenicity endpoint is:

• Anti-HPV immunoglobulin G (IgG) antibody geometric mean concentrations (GMCs), 1 month after the third dose (Month 7) for each antigen. For the derivation of GMC refer to section 7.6.

16.1.2. Intercurrent Event Handling and Data Imputation for Primary Immunogenicity Variable(s)

See Table A: and section 8.3.

16.1.3. Primary Analysis of Primary Immunogenicity Variables

The primary immunogenicity analysis will be performed for the PPS. If the number of participants excluded from the PPS is >5% when compared with the ES, then the analysis will also be performed for the ES.

The primary immunogenicity endpoint GMCs of anti-HPV IgG antibody concentration at Month 7 will be summarized by study group for each antigen with their 95% CI summarised for the pre-vaccination status of seronegative, seropositive and total. Anti-HPV IgG antibody concentration will be graphically presented by reverse cumulative curves per study group.

16.2. Secondary Immunogenicity

The secondary immunogenicity analyses will be performed for the PPS.

16.2.1. Secondary Immunogenicity Variables & Derivations

16.2.1.1. ANTI-HPV IGG ANTIBODY CONCENTRATION

Anti-HPV IgG antibody concentration at Day 1, Month 2, Month 3, Month 6, and Month 12 for each antigen.

Document: \\quintiles.net\Enterprise\Apps\sasdata\SAS\\SAS\GlaxoSmithKline\HPV\213749

(HPV9)\Biostatistics\Documentation\SAP\GSK 213749(HPV9-AS04-

001)_WZA97329_SAP_Final_v3.0_02FEB2024.docx

Author: PPD Version Number: 3.0

Version Date: 02FEB2024

Template No.: CS_TP_BS016 Revision 7 Reference: CS_WI_BS005

Page 35 of 48

16.2.1.2. ANTI-HPV IGG ANTIBODY SEROCONVERSION AND SEROPOSITIVITY RATE

Anti-HPV IgG antibody seroconversion and seropositivity rates at Day 1 (for seropositivity only), Month 2, Month 3, Month 6, Month 7 and Month 12 for each antigen.

Seroconversion is defined as the appearance of antibodies (i.e, concentrations greater than or equal to the cut-off value) in the serum of participants seronegative before vaccination.

Seropositivity is defined as the appearance of antibodies (i.e, concentrations greater than or equal to the cut-off value) in the serum of participants.

16.2.1.3. ANTI-HPV NEUTRALIZING ANTIBODY TITERS

Anti-HPV neutralizing antibody titers at Day 1, Month 3 and Month 7 (at least 150 participants in each group) and Month 2 in a subset of 384 participants (at least 96 in each group) for each antigen.

16.2.1.4. ANTI-HPV NEUTRALIZING ANTIBODY SEROCONVERSION AND SEROPOSITIVITY RATE

Anti-HPV neutralizing antibody seroconversion and seropositivity rates at Day 1 (seropositivity only), Month 3 and Month 7 (at least 150 participants in each group) and Month 2 in a subset of 384 participants (at least 96 in each group) for each antigen.

Seroconversion is defined as the appearance of antibodies (i.e, titer greater than or equal to the cut-off value) in the serum of participants seronegative before vaccination.

Seropositivity is defined as the appearance of antibodies (i.e, titer greater than or equal to the cut-off value) in the serum of participants.

16.2.1.5. CORRELATION BETWEEN ANTI-HPV IGG ANTIBODY CONCENTRATION AND ANTI-HPV NEUTRALIZING ANTIBODY TITERS

Correlation between anti-HPV IgG antibody concentrations and anti-HPV neutralizing antibody titers at Day 1, Month 2, Month 3, Month 7 and overall for each antigen.

Document: \\quintiles.net\Enterprise\Apps\sasdata\SASb\SAS\GlaxoSmithKline\HPV\213749

(HPV9)\Biostatistics\Documentation\SAP\GSK_213749(HPV9-AS04-

001)_WZA97329_SAP_Final_v3.0_02FEB2024.docx

Author: PPD Version Number: 3.0

Version Date: 02FEB2024

Template No.: CS_TP_BS016 Revision 7 Reference: CS_WI_BS005

Page 36 of 48

16.2.2. Intercurrent Event Handling and Data Imputation for Secondary Immunogenicity Variable(s)

See Table A: and section 8.3.

16.2.3. Analysis of Secondary Immunogenicity Variables

16.2.3.1. ANTI-HPV IGG ANTIBODY CONCENTRATION

The immunogenicity endpoint GMCs of anti-HPV IgG antibody concentration will be summarized for each antigen at Day 1, Month 2, Month 3, Month 6, and Month 12 by study group with their 95% CI derived considering log10-transformed antibody concentrations are normally distributed with unknown variance, summarised for the prevaccination status of seronegative, seropositive and total. The concentration below the assay cut-off will be assigned to half the cut-off for the purpose of GMC computation. The number of records above the ULOQ will be summarised at each visit for the pre-vaccination status of seronegative (except Day 1), seropositive and total.

Anti-HPV IgG antibody concentration will be graphically presented by reverse cumulative curves per antigen, timepoint and study group.

16.2.3.2. ANTI-HPV IGG ANTIBODY SEROCONVERSION AND SEROPOSITIVITY RATE

The percentage of participants with a seroconversion and seropositivity for each antigen will be summarized for each antigen at Day 1 (for seropositivity only), Month 2, Month 3, Month 6, Month 7 and Month 12 by study group and corresponding 2-sided 95% CI will be reported based on Clopper and Pearson method.

16.2.3.3. ANTI-HPV NEUTRALIZING ANTIBODY TITERS

The anti-HPV neutralizing antibody titers will be summarized for each antigen at Day 1, Month 3 and Month 7 (at least 150 participants in each group) and Month 2 in a subset of participants by study group with their 95% CI derived considering log10-transformed antibody titers are normally distributed with unknown variance, summarised for the pre-vaccination status of seronegative, seropositive and total. Anti-HPV neutralizing antibody titers will be graphically presented by reverse cumulative curves per antigen, timepoint and study group. The concentration below the assay cut-off will be assigned to half the cut-off for the purpose of GMT computation. The number of records above the ULOQ will be summarised at each visit for the pre-vaccination status of seronegative (except day 1), seropositive and total.

Document: \\quintiles.net\Enterprise\Apps\sasdata\SASb\SAS\GlaxoSmithKline\HPV\213749

(HPV9)\Biostatistics\Documentation\SAP\GSK_213749(HPV9-AS04-

001)_WZA97329_SAP_Final_v3.0_02FEB2024.docx

Author: PPD Version Number: 3.0

Version Date: 02FEB2024

Template No.: CS_TP_BS016 Revision 7 Reference: CS_WI_BS005

Effective Date: 01Nov2021

Page 37 of 48

16.2.3.4. ANTI-HPV NEUTRALIZING ANTIBODY SEROCONVERSION AND SEROPOSITIVITY RATE

The percentage of participants with a seroconversion and seropositivity for each antigen will be summarized at Day 1 (seropositivity only), Month 3 and Month 7 and Month 2 in a subset of 384 participants (at least 96 in each group) by study group and corresponding 2-sided 95% CI will be reported based on Clopper and Pearson method.

16.2.3.5. CORRELATION BETWEEN ANTI-HPV IGG ANTIBODY CONCENTRATION AND ANTI-HPV NEUTRALIZING ANTIBODY TITERS

The Pearson coefficient of correlation between anti-HPV IgG antibody concentration and anti-HPV neutralizing antibody titers with associated p-value will be calculated for each investigational adjuvanted vaccine groups and *Gardasil 9* group for each antigen at Day 1, Month 2, Month 3, Month 7 and overall. The Pearson correlation will be computed by the log10-transformation of specific antibody concentrations.

For each HPV type, the functional relationship between the pair of assay methods (pseudovirion-based neutralization assay [PBNA] verses electrochemiluminescence assay [ECL]) will be estimated by timepoint at Day 1, Month 2, Month 3 and Month 7 and overall using the Deming's regression model.

The Deming's regression will consider the following:

- Anti-HPV Neutralizing titers (from PBNA) with errors ϵ_i
- 1.1 $x_i = X_i + \epsilon_i$
 - Anti-HPV IgG antibody concentrations (from ECL) with errors δ_{ij}
- 1.2 $y_i = Y_i + \delta_i$

where X_i and Y_i are the measurements of Anti-HPV Neutralizing titers and Anti-HPV IgG antibody concentrations.

The Deming's regression model to be fitted is

$$Y = \beta_0 + \beta_1 X$$

The following terms will be fitted in the model:

Response (Y): log transformed anti-HPV IgG antibody concentration (from ECL)

Covariate (X): log transformed anti-HPV Neutralizing titers (from PBNA)

 β_0 is the Y-intercept and β_1 is the coefficient (slope) associated with the Anti-HPV Neutralizing titers from PBNA.

Document: \\quintiles.net\Enterprise\Apps\sasdata\SASb\SAS\GlaxoSmithKline\HPV\213749

(HPV9)\Biostatistics\Documentation\SAP\GSK 213749(HPV9-AS04-

001)_WZA97329_SAP_Final_v3.0_02FEB2024.docx

Author: PPD Version Number: 3.0

Version Date: 02FEB2024

Template No.: CS_TP_BS016 Revision 7 Reference: CS_WI_BS005

Page 38 of 48

Assumption: Error ratio: $V(\epsilon_i) / V(\delta_i) = 1$

The model will be fitted for each antigen and study group separately.

The intercept and the slope estimates and corresponding 95% CI (only for slope) will be presented. Note that a slope ≈ 1 implies a favorable outcome, i.e. both the assays (ECL and PBNA) are in strong agreement and have a similar performance.

Graphs representing the scatterplot of the Anti-HPV Neutralizing titers and Anti-HPV IgG antibody concentration will be presented for all timepoints with the Deming's regression line for each antigen and each study group. LLOQ and ULOQ values of the ECL and PBNA will also be presented in the same graph.

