 Pregnancy outcomes The percentage of participants who experienced pregnancy and their outcomes from Day 1 of pregnancy up to study end. Anti-HPV IgG antibody concentration at Day 1, Month 2, Month 3, Month 6, Month 7, and Month 12. Anti-HPV IgG antibody seroconversion¹ rate at
 Month 2, Month 3, Month 6, Month 7, and Month 12. Anti-HPV IgG antibody seroconversion¹ rate at
 Month 2, Month 3, Month 6, Month 7, and Month 12. Anti-HPV neutralizing antibody titers at Day 1, Month 3 and Month 7² in all participants, Month 2³ in a subset of participants. Anti-HPV neutralizing antibody seroconversion¹ rate at Month 3 and Month 7². Correlation between anti-HPV IgG antibody concentration and anti-HPV neutralizing antibody titers at Day 1, Month 2, Month 3, and Month 7.
tiary

- Seroconversion is defined as the appearance of antibodies (i.e., concentrations/titer greater than or equal to the cut-off value) in the serum of participants seronegative before vaccination.
- ² At least 150 participants in each group. In case of any delay, analysis may be performed for as many participants as possible with data available at the time of the analysis. Analysis for remaining participants will be performed at the time of the next analysis.
- ³ 384 participants (at least 96 participants in each group)

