9.2.2.1. Exploratory Immunologic Non-Inferiority Analyses

Exploratory immunologic non-inferiority analyses will be performed in the study, to help in decision making of the formulation selection for phase 3 (Table 18).

The estimated sample size of 216 evaluable participants in each group provides at least 94% power to evaluate non-inferiority of a formulation in terms of antibody geometric mean concentrations (GMCs) measured by the electrochemiluminescence (ECL) assay.

In order to control the global type I error to below 7.5%, Bonferroni correction will be applied. The non-inferiority of each of the investigational formulations will be assessed at 2.5% type I error. That is, the non-inferiority in terms of antibody GMC for the investigational formulation will be reached, if the lower limit of the 2-sided 95% CI for the antibody GMC ratio (investigational group/*Gardasil 9* group) is not less than 0.5 for each of the 9 HPV types. To account for the multiplicity of comparison for 9 HPV types, the global type II errors are conservatively estimated as the sum of individual type II errors.

Table 18 Power to Show That the Lower Limit of the 2-sided 95% CI on Anti-HPV IgG Antibody GMC ratio (HPV-9 Vaccine Group Divided by *Gardasil 9* Group), 1 Month After Dose 3 is Not Less Than 0.5

Standard deviation (Log ₁₀ [concentration])	N evaluable (in each group)	Type II error for each HPV type	Overall Power
0.7	216	0.6%	94.6%

CI = confidence interval; GMC = geometric mean concentration; HPV = human papillomavirus virus; IgG = immunoglobulin G

Power was obtained using PASS 2019, non-inferiority test for 2 means, under the alternative of equal means and variances.

Since there are no immunogenicity data generated with the assay that will be used in this study, several studies with various multivalent HPV formulations in the age group 16-26 years were reviewed and a conservative standard deviation for log₁₀ transformed antibody concentrations of 0.7 for each of the 9 HPV types is used for the computation of power.

If the standard deviation for \log_{10} transformed antibody concentrations is ≤ 0.47 , the sample size of 216 evaluable participants in each group provides at least 73% power to assess the non-inferiority of a formulation in terms of antibody GMCs with a non-inferiority margin of 0.67.

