The study also evaluates the **immune responses using a neutralization assay** as a secondary endpoint. If the standard deviation for log₁₀ transformed antibody titers is around 0.6 as observed in HPV-019 (109823) study assessing GSK's bivalent HPV-16/18 AS04-adjuvanted vaccine:

- the sample size of at least 150 participants to obtain 120 evaluable participants at Month 7 provides at least 74% power to assess the non-inferiority of a formulation to *Gardasil 9* in terms of neutralizing antibody geometric mean titers (GMTs) with a non-inferiority margin of 0.5.
- the sample size of at least 270 participants to obtain 216 evaluable participants provides at least 98% power to show the non-inferiority of a formulation to *Gardasil 9* in terms of neutralizing antibody GMTs with a non-inferiority margin of 0.5.

However, note that this does not take into account the multiplicity due to comparisons performed for antibody concentrations measured by ECL assay.

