9.4.2.2.1. Within Groups Assessment

For each group at each time point for which a blood sample result is available, the following analyses will be conducted:

- Seroconversion and seropositivity rates for each antigen (with exact 95% CI) will be calculated.
 - Seroconversion is defined as the appearance of antibodies (i.e., concentrations/titer greater than or equal to the cut-off value) in the serum of participants seronegative before vaccination.
- Antibody GMCs/GMTs with 95% CI and range of antibody concentrations/titers will be tabulated for each antigen.

- The antibody GMCs will be derived considering log-transformed concentrations are normally distributed with unknown variance. Concentration below the assay cut-off will be assigned half the cut-off for the purpose of antibody GMC computation.
- The distribution of antibody concentrations/titers for each antigen will be displayed using reverse cumulative curves for the sub-cohort of initially seronegative participants.
- Pearson coefficient of correlation between anti-HPV IgG antibody concentration and anti-HPV neutralizing antibody titers with associated P-value will be calculated for each investigational adjuvanted vaccines group and *Gardasil 9* group for each antigen for timepoint and overall. The Pearson correlation coefficient is computed by log₁₀ transformation of specific antibody concentrations. Scatter plots will be generated.
- For each HPV type, the functional relationship between the pair of assay methods (pseudovirion-based neutralization assay [PBNA] versus ECL) will be estimated by timepoint using the Deming's regression model (Brown et al, 2014).

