Secondary	Randomized HPV dose (High, Medium or Low) or Gardasil 9	Female participants between 16 and 26 years old	anti-HPV IgG antibody concentration and anti-HPV neutralizing antibody titers at Day 1, Month 2, Month 3 and Month 7	1. Permanently discontinuation from study treatment due to any reasons 2. Study vaccine not administered per protocol 3. Prohibited medication or intercurrent medical condition 4. Vaccine or blood	1. Missing data won't be imputed. 2. Participant excluded from the immunogenicity analysis. 3. Participant excluded from the immunogenicity analysis. 4. Participant excluded from the immunogenicity analysis. 5. Participant excluded from the immunogenicity analysis.	Correlation between anti-HPV IgG antibody concentration and anti-HPV neutralizing antibody titers for each timepoint. Functional relationship between each pair of assay methods. A qualitative summary between ECL and PBNA for each timepoint.

Document: \\quintiles.net\Enterprise\Apps\sasdata\SASb\SAS\GlaxoSmithKline\HPV\213749

(HPV9)\Biostatistics\Documentation\SAP\GSK 213749(HPV9-AS04-

001)_WZA97329_SAP_Final_v3.0_02FEB2024.docx

Author: PPD Version Number: 3.0

Version Date: 02FEB2024

Template No.: CS_TP_BS016 Revision 7 Reference: CS_WI_BS005

Effective Date: 01Nov2021

Statistical Analysis Plan

Page 18 of 48

Estimand	Attributes					
	Treatment	Population	Variable (or	Intercurrent events (ICEs)		Population level summary
			endpoint)	Description	Handling strategy	
				sample taken out of	analysis.	
				window		
				5. No post-vaccine		
				immunogenicity		
				result available		

Document: \\quintiles.net\Enterprise\Apps\sasdata\SASb\SAS\GlaxoSmithKline\HPV\213749

(HPV9)\Biostatistics\Documentation\SAP\GSK 213749(HPV9-AS04-

001)_WZA97329_SAP_Final_v3.0_02FEB2024.docx

Author: PPD Version Number: 3.0

Version Date: 02FEB2024

Template No.: CS_TP_BS016 Revision 7 Reference: CS_WI_BS005

Effective Date: 01Nov2021

Page 19 of 48

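### SAP 16.2.3.5 reads a Deming slope near 1 as strong agreement between ECL and PBNA, which the slope cannot show; the overall Pearson p-value and overall Deming interval also ignore repeated samples

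*SAP*

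**What the plan says.** SAP 16.2.3.5 plans two analyses of the relation between the assays, for each antigen and study group.

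- **Deming regression.** The response is log ECL concentration and the covariate is log PBNA titer, fitted at Day 1, Months 2, 3 and 7, and overall. The ratio of the two error variances is set to 1 under the label "Assumption: Error ratio", with no source in assay precision. A 95% CI is planned for the slope. The reading rule is: "Note that a slope ≈ 1 implies a favorable outcome, i.e. both the assays (ECL and PBNA) are in strong agreement". The sentence goes on to claim similar performance. It gives no band for what counts as near 1, and no condition on correlation, intercept or scatter.
- **Pearson correlation with p-value.** It is planned by visit and overall. Protocol 9.4.2.2.1 asks for it "for each antigen for timepoint and overall", and SAP 16.2.1.5 lists "Month 2, Month 3, Month 7 and overall for each antigen".

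The footnotes to shell Tables 14.2.2.6 and 14.2.2.7 define n as samples, so one participant can contribute up to four to an overall row. Neither document states a method for repeated samples. The endpoint in Protocol Table 4 is the correlation with "anti-HPV neutralizing antibody titers at Day 1, Month 2, Month 3, and Month 7", and SAP Table A defines the summary by visit: "anti-HPV neutralizing antibody titers for each timepoint".

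**The concern.** A Deming slope on log axes describes how one assay's log result scales with the other's. It does not describe how tightly the points follow the line. A plan that turns a slope near 1 into strong agreement could lead the report to describe two moderately related assays that way. The assays also measure different quantities (binding IgG concentration and neutralizing titer), so slope 1 with an arbitrary intercept is not agreement in value.

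The overall rows raise a separate problem. Samples from the same participant are correlated, so a p-value or interval that counts samples as independent is too optimistic. Pooling visits also builds the rise in antibody over time into the overall r, even if the assays were unrelated within each visit.

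**Working it through.** **1. Slope formula.** With error ratio 1, SDs sx (PBNA) and sy (ECL), and sxy = r·sx·sy:

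b = [sy² − sx² + √((sy² − sx²)² + 4·sxy²)] / (2·sxy)

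*Equal SDs.* sy² − sx² = 0, so b = 2·sxy / (2·sxy) = 1.00 for every r > 0.

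*Planning SDs.* Protocol 9.2.2.1 gives ECL 0.7 ("antibody concentrations of 0.7 for each of the 9 HPV types is used for the computation of power") and PBNA about 0.6 ("antibody titers is around 0.6 as observed in HPV-019 (109823) study"). Then sy² − sx² = 0.49 − 0.36 = 0.13.
- r = 0.5: sxy = 0.21; b = (0.13 + √(0.0169 + 0.1764)) / 0.42 = (0.13 + 0.4397) / 0.42 = 1.36.
- r = 0.99: sxy = 0.4158; b = (0.13 + √(0.0169 + 0.6916)) / 0.8316 = 1.17.

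**2. How often a moderate relationship gives a slope near 1.** Bivariate normal simulation, 20,000 runs per cell, r = 0.5, share of slopes in 0.9-1.1 (band chosen here):

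| SDs (ECL/PBNA) | n = 96 | n = 120 | n = 216 |
|---|---|---|---|
| Equal | 43% | 47% | 60% |
| 0.7/0.6 | 11% | 9% | 4% |

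**3. Overall Pearson p-value.** Protocol 4.1 plans PBNA in at least 96 participants per group at Month 2, all 270 at Month 3 and at least 150 at Month 7. With 20% non-evaluable (Protocol 9.2.2), that leaves 77, 216 and 120, or 413 samples. Day 1 is left out because the shell excludes samples below the LLOQ.

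Take the Month 2 and Month 7 subsets as drawn independently, and assume no true relation between the assays. Expected within-participant sample pairs: 77 (Months 2 and 3) + 120 (Months 3 and 7) + 77 × 120 / 216 = 42.8 (Months 2 and 7) = 239.8. With the same within-participant correlation ρ in both assays, the variance of r is inflated by about

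1 + ρ² × 2 × 239.8 / 413 = 1 + 1.161·ρ²

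| ρ (assumed) | Inflation | 1.96 / √inflation | Type I error at nominal 5% |
|---|---|---|---|
| 0.3 | 1.105 | 1.865 | 6.2% |
| 0.6 | 1.418 | 1.646 | 10.0% |
| 0.8 | 1.743 | 1.485 | 13.8% |

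Simulation at these counts agrees: about 6%, 10% and 13-14%.

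**4. Overall Deming interval.** In simulation with three samples from every participant, which is heavier repetition than planned, a sample-level 95% interval covered about 95%, 93-95% and 91-92% at ρ = 0.3, 0.6 and 0.8. The loss is small.

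**5. Overall r from pooling alone.** Assume log10 visit means of 3.0 and 3.3 at Months 3 and 7 in both assays, zero correlation within visits, and weights 77/413, 216/413 and 120/413. With between-visit variance V, r = V / √((V + 0.36)(V + 0.49)).
- Month 2 mean 1.5: V = 0.409, r = 0.49.
- Month 2 mean 2.0: V = 0.203, r = 0.32.
- Month 2 mean 2.5: V = 0.073, r = 0.15.

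**The case against.** **Other outputs would show a weak relationship.** This largely stands. The slope's own 95% CI is one safeguard. With equal SDs and an asymptotic interval (the SAP names no method), among runs with a slope in 0.9-1.1 at n = 96 the median interval is 0.54 to 1.83 at r = 0.3 and 0.70 to 1.41 at r = 0.5. Per-visit Pearson r and scatterplots are planned as well. SAP 16.2.4.5 adds kappa, though only on seropositive or seronegative status. These outputs limit the damage, but they do not make the sentence true.

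**The rule misleads in both directions.** A reader might infer this, since closely related assays with SDs 0.7 and 0.6 give a slope of about 1.17. The documents do not support it: the SAP never calls a slope away from 1 unfavourable. A log-log slope of 1.17 is also a real departure from proportionality.

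**Few slopes would land near 1 with the planning SDs.** True for 0.7 and 0.6. However, Protocol 9.2.2.1 calls 0.7 conservative and says there are no data from this assay, and the 0.6 comes from a study of a bivalent vaccine. Neither predicts the actual ratio.

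**The overall p-value hardly matters.** It tests zero correlation between two assays for the same HPV type, which is an unlikely null. If the assays are clearly correlated, the p-value is small either way. That stands, and the protocol itself requires this p-value. What remains is an interval and a p-value with no valid basis as specified, and an overall r that needs a caveat.

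**Conclusion.** The reading rule is wrong as written: a slope near 1 does not imply strong agreement. That follows from the algebra and does not depend on assumed SDs. How often the rule would mislead does depend on them: about 43-60% of slopes in the illustrative band at r = 0.5 with equal SDs, and about 4-11% with 0.7 and 0.6.

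The repeated-sample problem is real but moderate. At the planned minimum sampling, the type I error is about 6% to 14% over assumed within-participant correlations of 0.3 to 0.8. Pooling alone gives an overall r of about 0.15 to 0.49 over the assumed visit means. The documents give neither within-participant correlations nor visit means. If Day 1 samples above the LLOQ were kept, or more Month 2 and Month 7 samples tested, the inflation would be larger.

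A reader might also infer that formulation selection or the per-visit results are affected. The documents do not support that. Protocol 9.1 and 9.2.2.1 tie selection to the exploratory non-inferiority analyses, no decision rests on the slope, and by-visit rows hold one sample per participant. The consequence is confined to how a descriptive secondary result is worded and to its overall rows. This is worth correcting but does not threaten the trial's conclusions.

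**What to change.** - Delete the reading-rule sentence from SAP 16.2.3.5. Describe slope and intercept only as a scale relation between the log results.
- Judge strength of relationship at each visit from the planned Pearson r, adding its 95% CI, and from the scatterplot.
- Compute the overall Pearson p-value and the overall Deming CI by resampling participants. This keeps the p-value that Protocol 9.4.2.2.1 requires. Presenting the overall rows without p-values would also work, but departs from the protocol and needs an entry in SAP 4.3.
- Footnote the overall rows to say that r includes the rise in antibody over visits. Shell Table 14.2.2.8 also has an overall row that counts samples, so the repeated samples should be noted there too; no error rate was computed for it.
- Optional: a sensitivity range for the error ratio, for example half and twice, or a value from the assay qualification precision described in Protocol Appendix 3.

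The cost is one SAP sentence, a few shell footnotes and small program changes. No new data or samples are needed.
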